7.4.2 Dispensing

The Synvisc-One devices will be couriered to the Orthopaedic Institute by the UCSF investigational pharmacy according to subject enrollment by a pharmacy staff member. Upon device transfer from the pharmacy, the investigator shall maintain the devices at controlled room temperature in a designated area in a locked cabinet until they are released for patient administration upon the order of the investigator. The study investigators will administer the injections.

7.4.3 Administration Instructions

The syringe containing SYNVISC (hylan g-f 20) is intended for single use. The contents of the syringe must be used immediately after the syringe has been removed from its packaging. Precaution: Do not concomitantly use disinfectants containing quaternary ammonium salts for skin preparation because hyaluronan can precipitate in their presence. SYNVISC (hylan g-f 20) (2ml) is administered by intra-articular injection once a week (one week apart) for a total of three injections. Strict aseptic administration technique must be followed. Using an 18- to 22-gauge needle, remove synovial fluid or effusion before each SYNVISC (hylan g-f 20) (2ml) injection. Do not use the same syringe for removing synovial fluid and for injecting SYNVISC (hylan g-f 20) however the same 18- to 22-gauge needle should be used. Twist the tip cap before pulling it off, as this will minimize product leakage. To ensure a tight seal and prevent leakage during administration, secure the needle tightly while firmly holding the luer hub. Inject the full 2 mL in one knee only

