| | 
enrolled in the cohort will have baseline functional testing performed including a motion gait analysis, 12 minute walk test, and 3-day accelerometer data. Subjects will receive a single 6 mL intra-articular injection of hylan G-F 20 in the target knee at baseline. All ongoing treatments will be monitored at 6-month intervals over the 3-year duration of the study. Patients can receive any other conservative treatments (e.g., oral medications, physical or other therapy, acupuncture, etc., except other injection treatments) and current treatments will be documented during each patient encounter. An initial injection of hylan G-F 20 will be injected in the symptomatic knee using a standard supine lateral approach using a 20-gauge needle. A face-to-face follow up visit will be carried out 6 months after first injection with additional face to face meetings every 6 months thereafter unless the subject requires an additional injection of hylan G-F 20. Hylan G-F 20 treatments can be administered up to three times each year during the study duration. After each injection, follow up measures will be carried out using secure e-mail or phone contact at 6 weeks, 12 weeks, 18 weeks after each in-office evaluation or injection. Follow up will consist of WOMAC, Lysholm score, and Tegner score. Patients may return for retreatment of hylan G-F 20 if symptoms recur after at least 4 months following their previous injection and they meet the inclusion criteria for pain levels on the following WOMAC questions A1 (How much pain have you had walking on a flat surface?), C8 (How much difficulty have you had going down the stairs?), C9 (How much difficulty have you had when going up the stairs?), C10 (How much difficulty have you had when getting up from a sitting position?) and/or C23 (How much difficulty have you had while doing heavy household chores?). Inclusion criteria for pain level is defined by selecting moderate, severe, or extreme on all questions A1, C8, C9, C10 and/or C23. Those subjects who select mild or no pain levels on any of A1, C8, C9, C10 and/or C23, will not meet the criteria for WOMAC pain level and retreatment. Patients requiring three injections of hylan G-F 20 in 4 months or less will be allowed to exit the cohort after their six-month follow up following the third injection. Otherwise, patients will be followed until they reach the 3-year follow up, or drop out for other injection treatments or surgical treatment. Therefore, patients would potentially be able to receive up to 9 injections during the 3-year study.
 |

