| 
PRIMARY OBJECTIVES
 | 
Specific Aim 1: To identify whether injection of 6 mL hylan G-F 20 decreases pain over 26 weeks in young (ages 30 to 50 years) active patients with symptomatic primary osteoarthritis of the knee not treated previously with hylan G-F 20.
 |

| | |
|--|---|
| 
SECONDARY OBJECTIVES
 | 
Specific Aim 2: Though symptoms can be improved for periods up to 6 months, pain symptoms can recur. The effect of repeated treatments of hylan G-F 20 will be studied.
 
Specific Aim 3: To identify the effects of treatment with hylan G-F 20 on activity levels (using objective activity measures utilizing accelerometer and Physical Activity Enjoyment Scale (PACES) and quality of life scores (WOMAC, SF-12) comparing baseline to treatment at 3 months.
 
Specific Aim 4: To understand the natural history of conservative treatment on this cohort of patients over a 3 year period.
 |
| 
NUMBER OF SUBJECTS
 | 
150
 |
| 
SUBJECT SELECTION CRITERIA
 | 
Inclusion Criteria:
 
Male or female patients aged 30-50 years
 
History of symptomatic unilateral primary or secondary knee OA for more than 6 months
 
Signed written informed consent
 
Radiographic evidence of Kellgren-Lawrence Grade I or II OA of the target knee
 
Body Mass Index (BMI) < 30 kg/m²
 
Activity criteria (Tegner score > 3)
 
Continued target knee OA pain despite conservative treatment ≥ 3 months (e.g., weight reduction, physical therapy, analgesics)
 
Willing to withhold intake of NSAIDs (including COX-2 inhibitors) and analgesics, for a washout period of minimum 3 days up to 21 days prior to baseline visit (depending on medication)
 
Willing to discontinue prohibited treatments and medications throughout study period
 
Baseline inclusion criteria
 
 • Completed OA medication washout period • Target knee pain 4-8 (0-10 NRS) during most painful knee movement (Worst Knee Pain) • If female, must have had a negative urine pregnancy test and |

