7.4.1 Dosage/Dosage Regimen

Subjects will receive a single 6 mL intra-articular injection of hylan G-F 20 in the target knee at baseline. Patients can receive any other conservative treatments (e.g., oral medications, physical or other therapy, acupuncture, etc., except other injection treatments) and current treatments will be documented during each patient encounter. An initial injection of hylan G-F 20 will be injected in the symptomatic knee using a standard supine lateral approach using a 20 gauge needle. A face to face follow up visit will be carried out 6 months after first injection with additional face to face meetings every 6 months thereafter unless the subject requires an additional injection of hylan G-F 20. Hylan G-F 20 treatments can be administered up to three times each year during the study duration. After each injection, follow up measures will be carried out using secure e-mail or phone contact at 6 weeks, 12 weeks, 18 weeks after each in-office evaluation or injection. Follow up will consist of WOMAC, Lysholm score, and Tegner score. . Patients may return for retreatment of hylan G-F 20 if symptoms recur after at least 4 months following their previous injection and they meet the inclusion criteria for pain levels on the following WOMAC questions A1 (How much pain have you had walking on a flat surface?), C8 (How much difficulty have you had going down the stairs?), C9 (How much difficulty have you had when going up the stairs?), C10 (How much difficulty have you had when getting up from a sitting position?) and/or C23 (How much difficulty have you had while doing heavy household chores?). Inclusion criteria for pain level is defined by selecting moderate, severe, or extreme on all questions A1, C8, C9, C10 and/or C23. Those subjects who select mild or no pain levels on any of A1, C8, C9, C10 and/or C23, will not meet the criteria for WOMAC pain level and retreatment. Patients requiring three injections of hylan G-F 20 in 4 months or less will be allowed to exit the cohort after their six-month follow up following the third injection. Otherwise, patients will be followed until they reach the 3 year follow up, or drop out for other injection treatments or surgical treatment. Therefore, patients would potentially be able to receive up to 9 injections during the 3 year study.

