7.5 Supply of Study Drug at the Site

SYNVISC (hylan g-f 20) is supplied in a 2.25 mL glass syringe containing one 2 mL (16 mg) dose of hylan G-F 20. The contents of the syringe are sterile and non-pyrogenic. The injections will be sent in the standard approved market packaging, with one syringe per box. Replacements will be provided by the manufacturer per site request.

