8.1.8 Administration of Injection

Using an 18- to 22-gauge needle, the doctor will remove synovial fluid or effusion before each SYNVISC (hylan g-f 20) (2ml) injection. Using an 18- to 22-gauge needle, the doctor will inject the full 2 mL in one knee only.

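### 7.4.3 and 8.1.8 instruct 2 mL per injection, and 7.5 and 7.3.1 describe a 2 mL product, while Aim 1, the synopsis, 3.1 and 7.4.1 specify one 6 mL injection per treatment

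*Combined protocol and SAP*

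**What the plan says.** The intended treatment is stated consistently in several places. Aim 1, in the synopsis and again in 2.1, reads "To identify whether injection of 6 mL hylan G-F 20 decreases pain over 26 weeks". The study design part of the synopsis, 3.1 and 7.4.1 (Dosage/Dosage Regimen) each say "Subjects will receive a single 6 mL intra-articular injection of hylan G-F 20 in the target knee at baseline". Section 7.4.1 also sets the frequency. It allows retreatment only once at least four months have passed since the previous injection, states that "Hylan G-F 20 treatments can be administered up to three times each year during the study duration", and concludes that "patients would potentially be able to receive up to 9 injections during the 3 year study".

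Four other sections carry text for a 2 mL product:

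- 7.4.3 (Administration Instructions) says that SYNVISC 2 mL "is administered by intra-articular injection once a week (one week apart) for a total of three injections" and ends with "Inject the full 2 mL in one knee only".
- 8.1.8 (Administration of Injection) says that "the doctor will inject the full 2 mL in one knee only".
- 7.5 (Supply of Study Drug at the Site) says that SYNVISC "is supplied in a 2.25 mL glass syringe containing one 2 mL (16 mg) dose of hylan G-F 20", one syringe to a box.
- 7.3.1 (Formulation of Test Product) lists 16 mg of hylan polymers made up to 2.0 mL. It gives no composition for a 6 mL presentation.

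**The concern.** A dose conflict matters most where staff look for instructions. Sections 7.4.3 and 8.1.8 are current procedural text, and both give a volume that is not the one under test. Someone who follows them departs from 7.4.1, and someone who follows 7.4.1 departs from them. The monitor has no single written regimen to check against.

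This is a single-arm study. Its primary result is a responder proportion compared with a fixed 50% threshold, and it will be reported as the result of a 6 mL injection. If some subjects received 2 mL, or a weekly series, the proportion would mix treatments and no control arm would show it.

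**Working it through.** No sample-size or power figure is at issue, so there is no plan figure to reproduce. The check sets the dose statements side by side and does simple volume arithmetic.

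**1. Is the intended regimen clear?** Yes. Volume: 6 mL (Aim 1, synopsis, 3.1, 7.4.1). Injections per treatment, from 7.4.1: 3 treatments per year × 3 years = 9 treatments. The stated maximum is 9 injections, and 9 / 9 = 1 injection per treatment.

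**2. What does 8.1.8 give?** It states a volume per injection and no number of injections. Section 9 and Appendix 1 show one scheduled administration, at Visit 1. Read together, they give 2 mL at that visit: 2 / 6 = 33% of the intended volume, a shortfall of 6 − 2 = 4 mL.

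**3. What does 7.4.3 give?** 3 × 2 mL = 6 mL, or 100% of the intended volume, but in three injections on days 0, 7 and 14 instead of one. That conflicts with the rest of the plan in three ways:

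- *Interval.* 7.4.1 requires at least four months after the previous injection; 7.4.3 leaves seven days.
- *Maximum.* If each treatment took three injections, a ceiling of 9 would be used up in 9 / 3 = 3 treatments over three years. 7.4.1 allows up to three treatments in each year.
- *Visits.* Neither section 9 nor Appendix 1 has a week 1 or week 2 visit. This is supporting evidence only, because Appendix 1 also leaves out the on-demand retreatment injections.

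**4. Could 2 mL and 6 mL be two descriptions of one regimen?** Three 2 mL syringes at one visit would make 6 mL, but no text that could be seen tells staff to do that, and a 2.25 mL syringe cannot hold 6 mL. Section 7.3.1 names SYNVISC and Synvisc-One separately. Section 1.2 separates a series of three 2 mL preparations from the 6 mL preparation. The plan itself therefore treats them as different.

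**5. Does the dose enter the statistical calculations?** No. The inputs in the synopsis and in section 13 are the null rate of 0.50, the assumed responder rates, the one-sided 0.025 level and the number of subjects.

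**The case against.** The strongest reply is that the right dose is stated where one would look for it first. Section 7.4.1 is the dosing section, is as directive as 7.4.3 and 8.1.8, and says 6 mL. Most of 7.4.3 concerns technique, and its weekly sentence is about a named sister product. Sections 7.3.3, 7.4.2 and 7.6 name Synvisc-One as the product packaged, couriered and accounted for, and section 9 lists a Synvisc-One injection at Visit 1. There is one site, and the study investigators give the injections. If the device in hand is a single 6 mL unit, giving 2 mL would mean stopping a third of the way through. (That presentation is an assumption, since the plan does not print it.)

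Most of this stands, and it lowers the practical risk. It does not remove the conflict, because two procedural sections still state a different volume.

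Some stronger readings are tempting but not supported:

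- *That 7.4.3 and 8.1.8 are the only sections telling the injector how much to give.* Section 7.4.1 does so too, correctly.
- *That all four sections instruct a wrong dose.* Section 7.5 describes supply and 7.3.1 composition; neither instructs an injection.
- *That subjects could receive 27 injections (9 × 3).* This multiplies the 7.4.1 maximum by the 7.4.3 series, although 7.4.1 itself stops at 9 injections.
- *That there is a known shortfall in milligrams.* The plan prints no milligram content for the 6 mL product, so only volumes are compared here.
- *That Aim 2 is contradicted directly.* Aim 2 speaks of repeated treatments and names no volume.
- *That misdosing occurred.* The plan shows conflicting instructions, not what was given.

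**Conclusion.** The point holds as an internal inconsistency in operative text. It is wrong as written. It is not a questionable design choice, because the intended design of one 6 mL Synvisc-One injection per treatment is clear.

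Followed literally, the conflicting text gives between 33% of the intended volume (8.1.8 at Visit 1) and 100% of it in the wrong number of injections and on the wrong schedule (7.4.3). The 33% figure assumes that 8.1.8 is followed without reference to 7.4.1 and that the only injection is the scheduled one. Sample size, alpha and power do not change.

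One limit applies. The text immediately before 7.4.1 and the attached package insert were not available for this review. The finding is therefore that nothing visible reconciles the two regimens. Even so, the 2 mL wording would still stand in these sections and should be corrected.

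**What to change.** - In 7.4.3 and 8.1.8, replace the 2 mL instruction with one 6 mL Synvisc-One injection per treatment, given at one visit.
- In 7.4.3, delete the sentence describing three injections a week apart.
- In 7.5, replace the 2.25 mL syringe description with the Synvisc-One presentation.
- In 7.3.1, give the composition for Synvisc-One. Take this and the 7.5 presentation from its package insert, not by scaling up the 2 mL figures.

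The cost is a wording amendment to four sections with IRB approval. It adds no patients, visits or procedures and leaves the statistical analysis unchanged.

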7.5 Supply of Study Drug at the Site

SYNVISC (hylan g-f 20) is supplied in a 2.25 mL glass syringe containing one 2 mL (16 mg) dose of hylan G-F 20. The contents of the syringe are sterile and non-pyrogenic. The injections will be sent in the standard approved market packaging, with one syringe per box. Replacements will be provided by the manufacturer per site request.

7.5.1 Storage

Investigational Pharmacy

Study devices will be stored in protocol-specific bins on wire rack shelving units in a locked room (M69C) adjacent to the Investigational Drug Service office. Room temperature products are stored in protocol-specific bins on wire rack shelving units in a locked room (M69C) adjacent to the Investigational Drug Service office. Temperature is maintained between 20-25 degrees C. with occasional excursions within the range of 15-30 degrees C. as per the USP definition for Controlled Room Temperature. Two maximum/minimum thermometers (values recorded in whole degree C units) are used to track room temperature, one at the entrance and another at the other end of the storage racks; values are recorded on a daily basis. In addition, a Dickson temperature logger (values recorded every 5 minutes) is used to track temperatures on a continual basis.

The room is also subject to continual monitoring by Awarepoint, a wireless temperature monitoring system that sends text-page alerts to key personnel (pharmacist in charge in the main pharmacy and Investigational Drug Pharmacist) in the event of potential temperature excursions in storage areas. Awarepoint temperature sensors will send a page to the pharmacist in charge in the Inpatient Pharmacy and the PoR in the event of near excursions for all devices monitored by the Awarepoint system: room temperature, refrigerator and -20C freezer. In the event that the alarm is not addressed within 30 minutes, an alert is sent out to the Pharmacy manager on call. Max/min values are recorded daily on a month-specific paper record that is maintained in the room until the end of the month. After this, the records are stored in the IDS files. A copy of the logger readout is downloaded weekly and stored in the same IDS temperature files. The PoR will sign and date the temperature record and the printout of the logger data before filing. The

max/min thermometer at the door also measures relative humidity max/min. These values are recorded on the same record as the max/min temperatures. Reports from the system can be downloaded at any time for documentation of appropriate storage. Temperature monitoring devices are certified annually-biannually.

The PoR will secure the supplies while in possession of the pharmacy. Staff pharmacists have access to investigational agents; a copy of the key to the investigational drug storage room is on the narcotic key ring held by the Central Unit Dose pharmacist or narcotic technician on duty. Additional keys are in the possession of the IDS pharmacist and the Director of Pharmacy and 2 others are maintained in the IDS office, accessible to the Investigational Drug technician and IDS Pharmacists. Staff pharmacists have access to investigational agents; a copy of the key to the investigational drug storage room is on the narcotic key ring held by the Central Unit Dose pharmacist on duty. Additional keys are in the possession of the IDS pharmacist, the Director of Pharmacy and 2 others are maintained in the IDS office, accessible to the Investigational Drug technician and IDS Pharmacists. Limited key distribution as described.

Orthopaedic Institute

Upon transfer from the pharmacy, the investigator shall maintain the devices at controlled room temperature in a designated area in a locked cabinet at [name] until the investigator administrates them. Temperatures in the Orthopaedic Institute are also monitored using the AwarePoint system. AwarePoint enables the Investigational Pharmacy to monitor the Orthopaedic Institute's temperature remotely. Temperature is maintained between 20-25 degrees C. with occasional excursions within the range of 15-30 degrees C. as per the USP definition for Controlled Room Temperature. Study devices will be stored in the clinic until the protocol is closed or until their expiration date has been reached. In those events, those devices shall be returned to the pharmacy for final disposition. The investigator shall be responsible for maintaining the security of the material at the Orthopaedic Institute to prevent unauthorized use. Cabinet key access will be limited to investigators and study key personal.

7.6 Study Drug Accountability

The UCSF investigational pharmacy on the Parnassus campus will be responsible for study drug storage, handling, dispensing, record retention, and return of unused Synvisc-One. [name], investigational pharmacist, will be responsible for maintaining accurate records about devices received; facilitating the couriering of the devices to the investigative site; and returning devices to manufacturer as needed. An accurate and current accounting of the dispensing and return of study drug for each subject will be maintained on an ongoing basis by a member of the pharmacy staff. In supplement to paper based records, this pharmacy uses WebIDS/Vestigo, an internet based drug accountability system. The system will track inventory and expiration dates, generate prescription labels and recharge for services rendered.

At the Orthopaedic Institute, the devices will be locked in a secure cabinet and regularly monitored by [name]. [name] and study staff are responsible for maintaining adequate

records of the disposition of the drug including clinical the date, subject number, number of doses and amount dispensed. The number of study drug dispensed and returned by the subject will be recorded on the Investigational Drug Accountability Record. The study monitor will verify these documents throughout the course of the study.

7.7 Measures of Treatment Compliance

A member of the research team will contact the subjects every 6 weeks, either by email or phone, to assess for pain, other treatment history and any adverse events.

8 STUDY PROCEDURES AND GUIDELINES

A Schedule of Events representing the required testing procedures to be performed for the duration of the study is diagrammed in Appendix 1.

Prior to conducting any study-related activities, written informed consent and the Health Insurance Portability and Accountability Act (HIPAA) authorization must be signed and dated by the subject. If appropriate, assent must also be obtained prior to conducting any study-related activities.

8.1 Clinical Assessments

8.1.1 Concomitant Medications

All concomitant medication and concurrent therapies will be documented at each visit. Dose, route, unit frequency of administration, and indication for administration and dates of medication will be captured.

8.1.2 Demographics

Demographic information (date of birth, gender, race) will be recorded at screening visit.

8.1.3 Medical History

Relevant medical history, including history of current disease, other pertinent respiratory history, and information regarding underlying diseases will be recorded at screening visit.

